6.1.5. Analysis Visit Windows

For all analyses, unscheduled and/or repeated measurements will only be included if a scheduled measurement is not available and the unscheduled/repeated measurement falls within the analysis visit windows as described below ([Table 3](#) and [Table 4](#)). Otherwise, visits will be analyzed as scheduled.

Table 3: Visit Windows (Cohort 1)

Visit	Target Start Day	Lower Limit	Upper Limit
Screening	-14	-14	-1
Day 1	1	1	1
Day 2	2	2	2
Day 8	8	3	9

Table 4: Visit Windows (Cohort 2)

Visit	Target Start Day	Lower Limit	Upper Limit
1	-6	-6	-1
2	1	1	1
3	7	2	8
4	14	9	15
5	21	16	22
6	28	23	28
7	29	29	30
--	35	31	36

Visits should occur ± 1 day of the targeted date. The lower limit for each visit after Visit 2 (Day 1) starts 1 day after the upper limit for the previous visit (+1 of the targeted date).

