8.12 Safety Assessments

The Schedule of Visits and Assessments (Section 6) summarizes the clinical procedures to be performed at each visit. Individual clinical procedures are described in detail below. Additional evaluations/testing may be deemed necessary by the PI and/or the Sponsor for reasons related to subject safety.

This study assesses the safety and efficacy of ARQ-151 cream. Safety will be determined by evaluating physical examinations, application site reaction assessments, vital signs, ECGs, clinical laboratory parameters, and AEs as outlined in the Schedule of Visits and Assessments (Section 6). If deemed necessary, additional safety assessments will be performed at the discretion of the PI.

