8.12.4 ECG Monitoring

Single 12-lead ECGs will be performed at Screening for both Cohorts and at Baseline and Week 4 for Cohort 2.

ECGs will be performed on subjects in the supine position. All ECG tracings and readouts will be reviewed by the Study Physician or his/her designee.

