8.12.5 Laboratory Tests

All tests listed below will be performed according to the Study Events Flow Chart unless otherwise noted. The collection of specimens will be in a non-fasting state. In addition, laboratory safety tests may be performed at various unscheduled time points, if deemed necessary by the Investigator.

All tests listed below will be performed as follows:

Cohort 1: Screening and Day 2

Cohort 2 and Cohort 1 subjects who rollover into Cohort 2: Screening, Baseline, Week 2, and Week 4.

The collection of specimens will be in a non-fasting state. In addition, laboratory safety tests may be performed at various unscheduled time points, if deemed necessary by the PI.

Hematology

- Hemoglobin
- Hematocrit
- Total and differential leukocyte count
- Red blood cell count with indices and morphology
- Platelet count

Serum Chemistry

- Blood Urea Nitrogen
- Bilirubin (total and direct)
- Alkaline phosphatase
- Aspartate aminotransferase
- Alanine aminotransferase
- Albumin
- Sodium
- Potassium
- Chloride
- Glucose
- Creatinine

Urinalysis

- pH
- Specific gravity
- Protein*
- Glucose
- Ketones
- Bilirubin
- Blood*
- Nitrite*
- Urobilinogen
- Leukocyte esterase*

Additional Tests

- Urine drug screen**
 - Amphetamines
 - Barbiturates
 - Benzodiazepine
 - Cocaine
 - Cannabinoid
 - Methadone
 - Opiates
 - PCP
 - Propoxyphene
- Urine pregnancy test***
(for females only)

* If urinalysis is positive for protein, blood, nitrite and/or leukocyte esterase, a microscopic examination (for red blood cells, white blood cells, bacteria, casts, and epithelial cells) will be performed.

** Only at Screening visit

*** All visits for both Cohorts except Day 2 for Cohort 1

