9.3. Clinical Laboratory Evaluations

All summaries of laboratory values will be presented using SI units. All hematology, chemistry, urinalysis, and other results will be listed by subject and timing of collection. Abnormal results will be flagged in the listings.

Observed values and change from baseline at each time point for continuous hematology, chemistry, and urinalysis results will be summarized using descriptive statistics by visit and treatment within cohort. Categorical urinalysis results will be summarized using frequencies by visit and treatment within cohort. Shifts from baseline for clinical laboratory values below, within, or above the normal range will be provided for hematology, chemistry, and urinalysis results.

Pregnancy test results and hormonal laboratory results will be listed.

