14.3.4 Abnormal Laboratory Value		
NA		

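### SAP 6.1.5 leaves an unscheduled or repeat safety value out of the by-visit safety tables whenever the same window holds a scheduled value, and no worst-value summary is described to recover it

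*SAP*

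**What the plan says.** SAP 6.1.5 sets one rule for every analysis: "For all analyses, unscheduled and/or repeated measurements will only be included if a scheduled measurement is not available". A second condition follows, that "the unscheduled/repeated measurement falls within the analysis visit windows as described below". Safety data are not exempted.

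The protocol expects testing outside the schedule. Section 8.12 says "Additional evaluations/testing may be deemed necessary by the PI and/or the Sponsor for reasons related to subject safety", and section 8.12.5 says "laboratory safety tests may be performed at various unscheduled time points, if deemed necessary by the Investigator".

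For laboratory data, SAP 9.3 plans summaries by visit and adds: "Shifts from baseline for clinical laboratory values below, within, or above the normal range will be provided". The shift-table titles in SAP Table 7 (14.3.5.x) are by study visit. So are those for dermal response (14.3.6.1.x), vital signs and weight (14.3.6.2.x) and ECG interpretation (14.3.6.3). The entry "14.3.4 Abnormal Laboratory Value" in Table 7 is marked NA. SAP 6.1.8 sends all collected data to listings, and SAP 9.3 flags abnormal laboratory results there.

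Protocol 9.3 says that all laboratory, ECG and vital-sign results, with change from baseline, will be summarized. SAP Section 10 lists two departures from the protocol, on tube weight and on the depression severity categories. It does not list this one.

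**The concern.** One value per visit is what a repeated-measures efficacy model needs, and for efficacy the rule is sensible. Safety data differ, because an extra laboratory test, ECG or skin assessment is often done because something has caused concern. If such a value is abnormal and the scheduled value in the same window is normal, only the normal one is tabulated. A transient on-treatment abnormality then leaves no trace in the shift or frequency tables.

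Protocol 8.1.2 describes this as the first study of the cream in humans, and safety is part of the primary objective in both cohorts (Protocol 8.3.1). Transient findings are among the things the safety tables should show. The dermal response score matters particularly, because Protocol 8.11.2 ties treatment interruption to it.

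**Working it through.** There is no stated figure to reproduce. The check sets the windows in SAP Table 4 against the Cohort 2 schedule.

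**Inputs**
- Post-baseline windows to Day 28 (SAP Table 4): Visit 3 is Days 2-8 (7 days), Visit 4 is Days 9-15 (7), Visit 5 is Days 16-22 (7), Visit 6 is Days 23-28 (6). Total: 7 + 7 + 7 + 6 = 27 days.
- Laboratory tests (Protocol 8.12.5): "Screening, Baseline, Week 2, and Week 4". After baseline, that is Visits 4 and 6.
- ECG (Protocol 8.12.4): "Single 12-lead ECGs will be performed at Screening for both Cohorts and at Baseline and Week 4 for Cohort 2". After baseline, that is Visit 6 only.
- Vital signs (Protocol 8.12.3 and flow chart) and application-site scores (Protocol 8.12.6): Visits 3 to 6.

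**Days on which a scheduled value can displace an extra one** (sum of the lengths of the windows that hold a scheduled test)

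| Assessment | Windows with a scheduled test | Days exposed | Days on which the rule admits the value |
|---|---|---|---|
| Laboratory | 9-15, 23-28 | 7 + 6 = 13 of 27 (48%) | 27 - 13 = 14 |
| ECG | 23-28 | 6 of 27 (22%) | 27 - 6 = 21 |
| Vital signs, application-site scores | all four | 27 of 27 (100%) | 0 |

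These are counts of days on which displacement is possible if the scheduled test was done. They are not estimates of how often it would happen. A test after Day 36 falls in no window and so also stays out of the by-visit tables.

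**Three patterns, using a laboratory value**
1. *Abnormal extra value, normal scheduled value.* An enzyme is raised on Day 24 and in range at the scheduled sample on Day 28. Both days lie in the Visit 6 window and the scheduled value exists, so Day 24 is left out and Week 4 reads as within range. If Week 2 was also normal, the subject is within range in every scheduled post-baseline row.
2. *Abnormal scheduled value, normal repeat.* An enzyme is raised at the scheduled Day 14 sample and normal on repeat on Day 15. Day 14 stays, the repeat is dropped, and the table shows the abnormality.
3. *Extra value in a window with no scheduled test.* An enzyme is raised on Day 18. No laboratory test is scheduled at Visit 5, so the literal rule admits the value under that visit. Whether the tables have a row for it cannot be checked, because the shells are not in the public document.

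Only the first pattern understates abnormality.

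**The case against.** The strongest reply is that little is lost. All values are listed, abnormal laboratory results are flagged, and with about 92 subjects the listings can be read in full. The adverse event definition in Protocol 8.16.1.1 includes abnormal laboratory findings, and Protocol 9.3 rests the safety assessment mainly on treatment-emergent events, so a result that worries the investigator can reach the main safety display. Safety analyses are descriptive, and the by-visit tables are correct as by-visit tables. What is asked for is one more display.

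Most of this stands. A reader might infer that for-cause values survive only in a listing. The documents do not support that, given the adverse event route and the days on which the rule admits the value. A reader might also infer that the safety tables as a whole are biased toward safety. That is not shown either, because a confirmatory repeat leaves the abnormal scheduled value in place and nothing indicates which pattern would be more common. Nor can a rate of out-of-range blood pressure, heart rate or temperature be distorted, since SAP 9.4 plans no such rate. It plans descriptive summaries, and categories for weight change only.

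The reply does not dispose of the first pattern. The adverse event route depends on the investigator's judgment. For dermal scores, Protocol 8.12.6 requires the change to be judged worse than normal fluctuation before it is recorded. A shift table is useful because it does not depend on that judgment.

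**Conclusion.** The point holds as a limited gap. When a scheduled value exists in the same window, SAP 6.1.5 keeps the extra value out of the by-visit safety tables, and no worst-value or any-time summary is described. In Cohort 2 to Day 28 the exposure is 13 of 27 days for laboratory tests, 6 of 27 for ECGs, and 27 of 27 for vital signs and application-site scores. The understatement is confined to abnormal extra values whose scheduled counterpart is normal or less extreme. Such a value is then found only in the listings unless it is also reported as an adverse event.

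This rests on reading 6.1.5 literally and on table titles, because the shells were removed. The NA against 14.3.4 is weak support taken alone, since nothing says that entry would have been a summary table. The word all in Protocol 9.3 can be read loosely, but the SAP is narrower on its plain wording and Section 10 does not say so. The change is worth making because it is cheap; efficacy is not affected.

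**What to change.** Limit SAP 6.1.5 to the efficacy analyses and to the by-visit rows of the safety tables. State that worst post-baseline summaries use every scheduled, unscheduled and repeat value after first dose in the cohort, including values outside the Table 4 windows. Then add:

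- to the laboratory shift tables (14.3.5.x), a worst post-baseline column, with lowest and highest values handled separately so that a subject can count in both directions;
- to ECG interpretation (14.3.6.3), a worst post-baseline row, ordered normal, abnormal not clinically significant, abnormal clinically significant;
- to dermal response (14.3.6.1.x), a worst post-baseline row giving the highest score.

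Record in Section 10 that the by-visit rows use less than all results. State also whether 6.1.5 applies before dosing, since SAP 6.1.1 takes the last pre-dose observation as baseline without excluding unscheduled values.

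The cost is a few sentences and one column or row per table, from data already collected. The drawback is that subjects tested more often have more chances of an abnormal value. A footnote should say so and could give the number of subjects with unscheduled tests in each group.

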- i 4 mm skin punch biopsy for analysis of Roflumilast and metabolites (n = 15 for analysis). Tissue will be collected from at least 15 volunteer subjects; tissue collection will continue until samples have been collected from 5 subjects in each treatment group.
- j Telephone call to the subjects for follow up on any continuing adverse events related to study drug. Telephone call will also assess any emergent adverse event post Visit 6. Any emergent AEs will be followed in the clinic for up to one month at the investigator's discretion until resolved or otherwise judged as clinically stable.
- k Follow-up visits should occur within +/- 1 day of the targeted date.
- l For those subjects participating in the PK assessment, diary is completed by subject and reviewed by study staff during visit (Possible Side Reactions / Comments Section of the diary).

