8.5 Overall Study Design and Plan

There are 2 cohorts of subjects:

Cohort 1 is a single dose study to 25 cm² of psoriatic plaque(s) in up to up to 8 psoriasis subjects. Cohort 1 subjects may then be enrolled into Cohort 2 of the study if all admission criteria are met at the Baseline Visit (Day 1, Visit 2, per Cohort 2). In this case, the same plaque(s) treated in the Cohort 1 study may also be treated in Cohort 2.

Cohort 2 is a parallel group, double blind, vehicle controlled study in which ARQ-151 cream 0.5%, ARQ-151 cream 0.15% or vehicle cream is applied QD x 28 days to subjects with between 0.5% to 5.0% BSA of chronic plaque psoriasis.

Including both Cohorts, a total of up to 92 subjects will be enrolled at 7 study sites in Canada and 1 site in the U.S. Subjects will be adult (≥ 18 y/o) males or females with chronic plaque psoriasis. For inclusion into Cohort 2, subjects must have at least 1 target plaque of at least 9 cm² in size with TPSS ≥ 4 . While 1 target plaque is minimally acceptable, it is strongly recommended that 2 or 3 target plaques be identified, if present, meeting these criteria. Target plaques may be on the knees and/or elbows, but priority should be given to identifying target lesions in other areas. All psoriasis lesions on a subject will be treated in this Cohort except for those on the face, scalp, intertriginous areas, palms and soles.

Subject Participation

Cohort 1: This cohort involves a minimum of three clinic visits including Screening, Baseline, one follow-up visit (24 hours after the baseline visit) and one follow up telephone call 7 days after the follow up visit. Subjects may be asked to return for additional visits(s) if an adverse reaction occurs. The interval between the Screening and Baseline visits could be up to 14 days, therefore the anticipated maximum duration of subject participation in Cohort 1 is 22 days.

Cohort 2: This cohort involves a minimum of seven clinic visits including Screening, Baseline and four visits at Week 1, Week 2, Week 3 and Week 4 of treatment and a day 29 visit for a final PK collection. A follow-up telephone call with subjects will occur at week 5 to assess any reactions to discontinuing drug product and will decide upon disposition of any ongoing adverse events.

The interval between the Screening and Baseline visits could be up to 6 weeks, therefore the anticipated maximum duration of subject participation in Cohort 2 is 77 days.

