8.13 Efficacy Evaluations (Cohort 2 Only)

8.13.1 Product of the Target Plaque Severity Score (TPSS) and the Target Plaque Area (TPA)

Target Plaque Severity Score (TPSS) will be determined for each target plaque on each subject as the sum of erythema (graded 0-4), thickness (graded 0-4), and scaling (graded 0-4) using the descriptors listed below.

Erythema

0 = none (includes hyperpigmentation)

1 = Mild - faint redness

2 = Moderate - red

3 = Severe - Bright red / dark red

4 = Very Severe - Extremely dark red / purple

Thickness

0 = none - no elevation over normal skin

1 = Mild - slight elevation

2 = Moderate - moderate elevation with rough or sloped edges

3 = Severe - marked elevation with hard or sharp edges

4 = Very Severe - very marked elevation with hard and sharp edges

Scaling

0 = none

1 = Mild - fine scale that covers part ($\leq 50\%$) of the lesion

2 = Moderate - fine to rough scale that covers a large part ($>50\%$) of the lesion

3 = Severe - rough, thick scale that covers almost all the lesion

4 = Very Severe - very rough, very thick scale that completely covers the lesion

Target plaque area (cm^2) is determined by multiplying the longest diameter (cm) of the target plaque by the widest perpendicular diameter (cm) (perpendicular to the longest diameter of the target plaque). The same plaque(s) will be measured at each applicable visit. If a plaque is resolved after baseline with a score of 0 for all descriptors (i.e., Erythema, Thickness and Scaling), then the TPSS x TPA should be recorded as 0.

Values for TPSS and measurement of the Target Plaque Area will be calculated at Screening, Baseline, Visit 3, Visit 4, Visit 5 and Visit 6.

Investigators should aim to identify up to 3 target plaques of at least 9 cm² in size with TPSS ≥4. One or two target plaques are acceptable, but only if a subject does not have three plaques meeting the criteria of at least 9 cm² with a TPSS ≥4. Target plaques may be on the knees and/or elbows, but priority should be given to identifying target lesions in other areas.

Whenever possible, the same individual who performs the target plaque analyses for a subject at baseline should continue to perform the analyses for that subject during the course of the study.

Changes in Target Plaque Severity Scores consistent with disease fluctuation, will only be recorded as an AE if the Investigator considers the change to be worse than normal fluctuation.

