3.1. Overall Design

There are 2 cohorts of subjects:

Cohort 1

Cohort 1 is an open label, single dose study to 25 cm² of psoriatic plaque(s) in up to up to 8 subjects with psoriasis. Cohort 1 subjects may then be enrolled into Cohort 2 of the study if all admission criteria are met at the Baseline Visit (Day 1, Visit 2, per Cohort 2). In this case, the same plaque(s) treated in the Cohort 1 study may also be treated in Cohort 2; however, a minimum of 14 days of wash-out is required between Cohort 1 drug application and the baseline visit of Cohort 2. This cohort involves a minimum of 3 clinic visits including Screening, Baseline, 1 follow-up visit (24 hours after the baseline visit) and 1 follow up telephone call 7 days after the follow up visit. Subjects may be asked to return for additional visits(s) if an adverse reaction occurs. The interval between the Screening and Baseline visits could be up to 14 days, therefore the anticipated maximum duration of subject participation in Cohort 1 is 22 days.

Cohort 2

Cohort 2 is a parallel group, double blind, vehicle controlled study in which ARQ-151 cream 0.5%, ARQ-151 cream 0.15% or vehicle cream is applied QD x 28 days to subjects with 0.5% to 5.0% BSA of chronic plaque psoriasis, inclusive. This cohort involves a minimum of seven clinic visits including Screening, Baseline and 4 visits at Week 1, Week 2, Week 3, and Week 4 of treatment and a Day 29 visit for a final PK collection. A follow-up telephone call with subjects will occur at Week 5 to assess any reactions to discontinuing drug product and will decide upon disposition of any ongoing AEs. The interval between the Screening and Baseline visits could be up to 6 weeks, therefore the anticipated maximum duration of subject participation in Cohort 2 is 77 days.

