6.1. Statistical Definitions and Algorithms

6.1.1. Baseline

The last observation recorded before the first dose of study drug in each cohort will be used as the baseline observation for all calculations of change from baseline.

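### Two limits in SAP Table 4 are wrong: the Visit 6 window omits Day 29, and the Cohort 2 screening window gives weeks as days

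*SAP*

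**What the plan says.** SAP 6.1.5 gives the windows a limited role. For all analyses, "unscheduled and/or repeated measurements will only be included if a scheduled measurement is not available" and the value falls inside the window for that visit. The section adds: "Otherwise, visits will be analyzed as scheduled".

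The text under Table 4 repeats the one-day visit tolerance and says that each lower limit after Visit 2 "starts 1 day after the upper limit for the previous visit (+1 of the targeted date". The tolerance comes from footnote k of the Cohort 2 flow chart in protocol section 6: "Follow-up visits should occur within +/- 1 day of the targeted date".

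Three rows of Table 4 matter here:
- Visit 1: target -6, limits -6 to -1
- Visit 6: target 28, limits 23 to 28
- Visit 7: target 29, limits 29 to 30

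SAP 3.1 describes the last of these as a "Day 29 visit for a final PK collection". Plaque assessment stops one visit earlier (protocol 8.13.1): "Values for TPSS and measurement of the Target Plaque Area will be calculated at Screening, Baseline, Visit 3, Visit 4, Visit 5 and Visit 6".

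On screening, protocol 8.5 states: "The interval between the Screening and Baseline visits could be up to 6 weeks". SAP 3.1 says the same.

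Baseline has its own rule in SAP 6.1.1: "The last observation recorded before the first dose of study drug in each cohort will be used as the baseline observation".

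**The concern.** Visit 6 is the primary time point, and it is the only visit from Visit 3 on whose window stops on the target day itself. A value taken one day late, within the tolerance for the visit, is labelled Visit 7 if it was recorded as unscheduled or repeat. The flow chart lists only PK sampling and a diary review at Visit 7. A plaque score, laboratory result, ECG, vital sign or QIDS-SR value sent there would have no planned place in the by-visit analyses.

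The screening row looks like a unit slip. The value -6 is the entry in the Weeks row of the Cohort 2 schedule, but Table 4 is expressed in days.

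SAP 6.1.4 says missing data are in general not imputed. When a scheduled value is missing, Table 4 therefore decides whether a substitute enters the analysis, and a programmer will code the limits as printed.

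**Working it through.** **Inputs.** Targets and limits come from SAP Table 4, the limit rule and tolerance from the text beneath it, the screening length and maximum participation from SAP 3.1, and the Cohort 1 comparison from SAP Table 3.

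**Step 1: apply the SAP's own rule.** Upper limit = target + 1. Lower limit = previous upper limit + 1, for visits after Visit 2.

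| Visit | Target | Table 4 limits | Target + 1 | Upper agrees? | Previous upper + 1 | Lower agrees? |
|---|---|---|---|---|---|---|
| 3 | 7 | 2 to 8 | 8 | yes | 1 + 1 = 2 | yes |
| 4 | 14 | 9 to 15 | 15 | yes | 8 + 1 = 9 | yes |
| 5 | 21 | 16 to 22 | 22 | yes | 15 + 1 = 16 | yes |
| 6 | 28 | 23 to 28 | 29 | **no** | 22 + 1 = 23 | yes |
| 7 | 29 | 29 to 30 | 30 | yes | 28 + 1 = 29 | yes |
| Week 5 call | 35 | 31 to 36 | 36 | yes | 30 + 1 = 31 | yes |

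Eleven of the twelve limits reproduce. The Visit 6 upper limit does not: Day 28 is printed and the rule gives Day 29. With the one-day tolerance Visit 6 may fall on Days 27 to 29, and Table 4 covers only Days 27 and 28 of these.

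**Step 2: see whether the rule can hold for Visit 6.** Applied literally, it gives Visit 6 Days 23 to 29 and Visit 7 Day 30 only. Visit 7 then excludes its own Day 29 target. The two targets are one day apart, so a single set of non-overlapping windows cannot give both visits target + 1. The windows have to differ by type of assessment.

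**Step 3: screening.** 6 weeks x 7 = 42 days. The SAP's maximum participation of 77 days confirms this: 42 + 35 = 77. Table 4 covers Days -6 to -1, which is 6 days. The remainder, 42 - 6 = 36 days (Days -42 to -7), lies in no window. Table 3 gives Cohort 1's 2-week screening as -14, that is 2 x 7. The conversion was made for Cohort 1 and not for Cohort 2.

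**Step 4: who is affected.** A Day 29 value is lost to Week 4 only if the scheduled Visit 6 value is missing and the Day 29 value is unscheduled or repeat. For screening, the measure that matters most is QIDS-SR. Its only scheduled pre-dose assessment is at Screening (protocol 8.14), and SAP 9.6 plans a shift from baseline. If that assessment is missing, 6.1.5 bars an unscheduled or repeat value from Days -42 to -7, whereas the baseline rule in 6.1.1 read alone would accept it.

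**Step 5: lower limits.** Day 23 is 2 days from the Week 3 target and 5 from the Week 4 target. Day 24 is 3 and 4 days away respectively. Both days are assigned to Week 4, as the stated rule requires. Days 9 and 10, and Days 16 and 17, show the same pattern.

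**The case against.** The strongest reply is that 6.1.5 applies the windows only to unscheduled or repeat values when no scheduled value exists. A reader might infer from Table 4 that an on-time Week 4 visit on Day 29 is discarded. The documents do not support that: the tolerance concerns scheduled visits, and 6.1.5 analyses those as scheduled. This part of the reply stands in full.

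A reader might also infer that the lower limits contradict the rule because Days 23 and 24 lie nearer to Week 3. They do not, because every lower limit follows the stated rule. Midpoint limits are a design preference.

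Nor does the screening slip disturb the efficacy baseline. TPSS x TPA is scheduled again at Baseline, and SAP 6.1.1 takes the last pre-dose observation without reference to the Visit 1 window.

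The Visit 6 limit also has an evident cause, since Day 29 is the target of Visit 7. That explains the entry but does not remove the gap. Day 29 is needed at Visit 7 for PK, yet the table takes it away from every other assessment as well.

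Finally, the documents provide for unscheduled laboratory tests and additional safety assessments but mention no unscheduled plaque assessment, so the route to the primary endpoint may seldom or never be used. An MMRM also keeps a subject who has earlier visits and no Week 4 value. Both points are fair and limit the size of the effect.

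**Conclusion.** Two entries in Table 4 are wrong as written: the Visit 6 upper limit, and the Cohort 2 screening limits. The first rests on the SAP's own rule and the one-day tolerance. The second rests on the 6-week screening period, with weeks entered as days as the likely explanation.

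The expected effect on the primary result is small. The documents give no count of affected subjects. For scale only, 84 randomised 1:1:1 is 28 per arm against 24 in the power calculation, a planning allowance of 28 - 24 = 4 per arm for dropout. Those affected at Week 4 would need a missing scheduled value and also an unscheduled or repeat plaque assessment on Day 29. Such a subject would still contribute earlier visits to the MMRM. With no imputation, the subject would contribute nothing to a Week 4 ANCOVA.

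The Day 23 and 24 assignment is not an error. It does let an unscheduled value taken 4 or 5 days early stand in for the primary time point, while one taken a day late cannot.

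**What to change.** In SAP 6.1.5:

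- Set the Cohort 2 screening window to Day -42 to Day -1.
- Set the Visit 6 upper limit to at least Day 29 for all non-PK assessments, and restrict the Visit 7 window to PK.
- State where a non-PK value on Day 30 belongs. If Visit 6 ends on Day 29 and the Week 5 window starts on Day 31, such a value would otherwise have no window.
- Amend the sentence under Table 4 to match, since one rule can no longer describe both visits.

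Optionally, replace the lower limits by midpoints: Visit 3 Days 2 to 10, Visit 4 Days 11 to 17, Visit 5 Days 18 to 24, Visit 6 from Day 25. This also requires rewriting the lower-limit rule.

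The cost is one table, split by type of assessment, and the text beneath it. Data collection does not change. The edit should be made before unblinding, because a later choice about which values count as Week 4 could depend on the data.
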